**P15-743 (HCV RWE)\_ STATISTICAL ANALYSIS PLAN \_ final 2.0 \_ 02 Feb 2018**

Similar to table 2.1.1.3, the following table will be constructed:

Table 2.1.1.4. Percentage for effectiveness endpoints without patients with missing SVR12 (additional analysis)

If the target population and the core population with sufficient follow-up data will not be equal to the core population, the following tables will be presented:

Table 2.1.2.1. Percentage for effectiveness endpoints (main analysis)

The target population

Table 2.1.2.2. Percentage for effectiveness endpoints (additional analysis)

The target population

Table 2.1.2.3. Percentage for effectiveness endpoints without patients with missing SVR12 (main analysis)

The target population

Table 2.1.2.4. Percentage for effectiveness endpoints without patients with missing SVR12 (additional analysis)

The target population

Table 2.1.3.1. Percentage for effectiveness endpoints (main analysis)

The core population with sufficient follow-up data

Table 2.1.3.2. Percentage for effectiveness endpoints (additional analysis)

The core population with sufficient follow-up data

Table 2.1.3.3. Percentage for effectiveness endpoints without patients with missing SVR12 (main analysis)

The core population with sufficient follow-up data

Table 2.1.3.4. Percentage for effectiveness endpoints without patients with missing SVR12 (additional analysis)

The core population with sufficient follow-up data

**P15-743 (HCV RWE) \_ STATISTICAL ANALYSIS PLAN \_ final 2.0 \_ 02 Feb 2018**

Abbvie LLC  
P15-743 (HCV RWE)  
**Table 2.2.1.1.1. SVR12 achieving response. Univariate logistic regressions results**  
The core population  
Page X of X

|                              | Overall               |
|------------------------------|-----------------------|
| Age                   |                       |
| Patients for analysis (n)    | XXX                   |
| Convergence criterion status | XXXXXXXXXXXX          |
| OR (95% Wald CI)             | X.XXX (X.XXX - X.XXX) |
| p-value                      | 0.XXXX                |
| Sex                   |                       |
| Patients for analysis (n)    | XXX                   |
| Convergence criterion status | XXXXXXXXXXXX          |
| Reference level              | XXXXXX                |
| OR (95% Wald CI) for Male    | X.XXX (X.XXX - X.XXX) |
| p-value for Male             | 0.XXXX                |
| ...                          | ...                   |

SVR12: sustained virological response at 12 weeks after EoT.

Program code, date, time

Data extracted: DD.MM.YYYY

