9.7.3.3 Statistical Methods for Analysis of Effectiveness Variables

The simple percentage of patients achieving SVR12 will be calculated and an exact two-sided 95% confidence interval (CI) of the percentage will be computed based on the Clopper-Pearson method.

Corresponding methods will be used for other response rates (EoT response rate, relapse rate, viral breakthrough). The relapse rates will be estimated in patients of the CP analysis groups with EoT response and sufficient HCV RNA measurements post-

treatment. Viral breakthrough rates will be estimated in all patients of the CP analysis groups, who have at least one undetectable HCV RNA measurement on-treatment and at least one on-treatment or EoT measurement thereafter.

Univariate and multiple logistic regression (MLR) methods will be used to investigate the impact of the following explanatory covariates on SVR12:

- Key demographic information
- Mode of CHC infection
- HCV RNA level at baseline
- Most recent stage of liver fibrosis
- HCV genotype and subtype (if available)
- Type of treating institute
- Liver and/or CHC related co-morbidities
- Key clinical chemistry and hematology laboratory variables at baseline
- In treatment experienced patients only:
 - Most recent prior treatment for CHC
 - Outcome of most recent prior CHC treatment

Further details and additional covariates will be specified in the SAP.

These analyses will be of exploratory nature, data driven, and will be repeatedly performed for various CP Analysis Groups, since not each covariate might be predictive in each patient group. Furthermore, the fact that treatment regimens will differ in the various patient groups has to be taken into account, when selecting the patient groups for each MLR analysis. Backward selection procedures will be applied to generate the final MLR models which consider only covariates in the selection procedure with a p-value <0.25 in the corresponding univariate logistic regression analysis. A p-value <0.05 will be used for the covariates to stay in the model in a backward elimination step. Logistic regression methods will also be used to investigate the impact of treatment adherence on SVR12.

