### **7.2 Statistical tests and common calculations**

Unless otherwise specified in the description of the analyses, the following arrangements will be applied:

- all tests will be two-sided with the default significant level 5%;
- confidence intervals will be 95% and will be determined using the Clopper-Pearson method.

Type I error values (p-values) will be rounded to four decimal symbols.

For quantitative measurements of clinical laboratory data, changes from baseline will be calculated as (measurement at visit X – measurement at baseline).

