- key demographic information:
  - age;
  - gender;
  - race;
- mode of CHC infection:
  - Most likely mode of HCV infection;
  - HCV Genotype and Subtype;
- HCV RNA level at baseline;
- most recent stage of liver fibrosis:
  - Severity of cirrhosis by Child-Pugh classification;
  - Result of FibroTest;
  - ISHAK Fibrosis Score;
  - METAVIR Fibrosis Score;

- BATTIS/LUDWIG Fibrosis Score;
- KNOPELL Fibrosis Score;
- SCHEUER Fibrosis Score;
- liver and/or CHC related co-morbidities;
- treatment experience (Interferon, Ribavirin, DAA);
- outcome of most recent prior CHC treatment
- laboratory hematology:
  - hemoglobin;
  - platelets;
  - prothrombin time, international normalized ratio (INR);
- laboratory clinical chemistry:
  - ALT;
  - AST;
  - gamma-GT;
  - total bilirubin;
  - albumin;
  - creatinine clearance;
  - alpha-1-fetoprotein.

After univariate model analyses all covariates with a p-value <0.25 in the corresponding univariate logistic regression analysis will be included to multiple logistic regression (MLR) model. MLR will be performing only if more than one explanatory variables will have a p-value <0.25 in the univariate model analyses.

Statistical significant correlated variables with correlation coefficient  $\geq 40$  should be considered and managed. All solutions about choosing explanatory variables will be of exploratory nature, data driven, and will be described with presenting of results of the “*PROC CORR*” SAS procedure.

Backward selection procedures will be applied to generate the final MLR models. A p-value <0.05 will be used for the covariates to stay in the model in a backward elimination step.

The SAS procedure LOGISTIC will be used for the analysis with following statements:

- SELECTION= BACKWARD;
- SLENTRY=0.05.

To avoid the multicollinearity problem all possible explanatory variables will be examined using following SAS script:

```
ods graphics on;  
PROC CORR data=<dataset> plots=all;  
  VAR <variables>;  
RUN;  
ods graphics off;
```

All data for Effectiveness Analyses will be listed in separate listings (for each effectiveness analyses endpoint). Additional listings for NCP population will be created.

---

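### The p<0.25 predictor screen names no test and has no rule for separation; if the Wald p-value is used, a two-level predictor with no failures in one level is dropped however strong it is

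*SAP*

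**What the plan says.** SAP section 9 fits one-covariate logistic models and then states that "all covariates with a p-value <0.25 in the corresponding univariate logistic regression analysis will be included to multiple logistic regression (MLR) model". Protocol 9.7.3.3 has the same rule: the final models "consider only covariates in the selection procedure with a p-value <0.25 in the corresponding univariate logistic regression analysis". Both rules work per covariate. Neither names the test (Wald, score or likelihood ratio), and neither says which p-value represents a covariate with several levels.

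The shell for these fits, SAP Table 2.2.1.1.1, shows Age and Sex and then continues with an ellipsis. For Sex it has a reference level, "OR (95% Wald CI) for Male" and "p-value for Male". Only the interval is labelled Wald. No overall-test row is shown for a categorical covariate. There is a row for "Convergence criterion status", but no action is attached to it.

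For backward elimination, "A p-value <0.05 will be used for the covariates to stay in the model in a backward elimination step", again without naming the test. The software is fixed ("The SAS procedure LOGISTIC will be used for the analysis with following statements"), and no exact or penalised option is given.

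**The concern.** When one level of a covariate has no SVR12 failures, its maximum-likelihood odds ratio is infinite (separation). The fitted log odds ratio grows, its standard error grows far faster, and the Wald p-value goes to about 1 however strong the evidence is. A screen on that p-value then rejects the covariate, even at a threshold as lenient as 0.25.

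This matters because predictive factors of virological response are secondary objective 2 and failures are expected to be few. Protocol Table 1 reports SVR12 of 97-100% in genotype 1b and 90-97% in 1a for non-cirrhotic patients, and HCV genotype/subtype is a listed covariate. The fits are also repeated by ribavirin use, Child-Pugh class and treatment experience, and for breakthrough, relapse, failure to suppress and end-of-treatment response. These repeats spread the few events more thinly.

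**Working it through.** **1. How many failures the plan implies.** Protocol 9.5 and SAP 4.2 give 158 evaluable patients, SVR12 of 90% and a Clopper-Pearson interval of 84.2% to 94.2%. Taking x = 0.90 × 158 = 142.2, the beta quantiles give 84.23% to 94.20% (width 9.97), so the stated figure is reproduced. Failures are then 0.10 × 158 = 15.8, about 16. At the protocol's alternative rate of 95% they are about 8. With no association, a level of 20 patients has no failures with probability 0.90^20 = 0.12 or 0.95^20 = 0.36.

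**2. One separated table.** The documents give no cell counts, so the split is an assumption: failures 0/79 v 8/79.

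- Wald: the fit stops at b = 18.02 with SE = 2743, so z = 0.0066 and p = 0.995.
- Likelihood ratio (LR): null log-likelihood 8 ln(8/158) + 150 ln(150/158) = -31.66. Fitted log-likelihood 8 ln(8/79) + 71 ln(71/79) + 0 = -25.90. LR = 2 × 5.76 = 11.52 on 1 df, p = 0.0007. Fisher's exact p = 0.0065.

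Other two-level tables with an empty level behave alike: 0/50 v 16/108 gives Wald 0.993 and LR 0.0003; 0/20 v 16/138 gives Wald 0.994 and LR 0.032. Without separation (4/79 v 12/79) the tests agree: Wald 0.044, LR 0.031.

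**3. Three levels.** Failures 12/60, 4/50, 0/48, LR p = 0.0004.

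- Reference = first level: level p-values 0.085 and 0.993, so one passes.
- Reference = zero-failure level: 0.993 and 0.994, so neither passes.
- Joint Wald p = 0.227 under any reference, which just passes.

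**4. How often it matters.** For two levels, sum over failure counts a and c the product Bin(a; n1, 1-p1) × Bin(c; n2, 1-p2) for every table whose p-value is below 0.25. All rates and splits are assumptions. A missing fraction m counted as failure multiplies each rate by (1-m).

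| Patients; SVR12 by level | Pass by Wald | Pass by LR |
|---|---|---|
| 79 v 79; 99.5% v 92% | 27% | 95% |
| 118 v 40; 99.5% v 92% | 35% | 88% |
| 40 v 40; 99% v 90% | 17% | 84% |
| 79 v 79; 97% v 92% | 50% | 63% |
| Row 1 with 3% missing (96.5% v 89.2%) | 69% | 77% |
| Row 1 with 5% missing (94.5% v 87.4%) | 66% | 68% |
| 79 v 79; 95% v 85% (overall 90%) | 83% | 85% |

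In row 1 a level is empty in about 0.995^79 = 67% of data sets, and those are the covariates that Wald loses.

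**The case against.** A reader might infer that the SAP prescribes level-specific Wald p-values for the screen. The documents do not say so: the rule is per covariate, the test is unnamed, and only the interval carries the Wald label. The shell's one categorical example has two levels, where the level p-value is itself the overall test, and no multi-level covariate is shown. This stands. The Wald reading is the natural one, because that p-value is the only one specified and sits beside a Wald interval, but it is an inference.

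A second tempting reading is that level-specific p-values cause the loss. For two-level covariates they do not; the cause is the Wald test under separation. For three or more levels a covariate is not generally discarded, as step 3 shows.

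Third, protocol 9.7.1 counts HCV RNA that is still missing as failure, and the main effectiveness shell lists missing SVR12 data among the non-response rows. Such failures fall in every level and fill empty cells, and the plan assumes 90% overall. This also stands and limits the size. It does not help in small levels or subgroups, or in an analysis that excludes missing SVR12. SAP 7.3 says that no data will be imputed, and section 9 does not say which rule the regressions follow.

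Fourth, null multi-level covariates could enter too easily on their smallest level p-value. In a simulation with 16 failures in 158 and five equal levels, this happened in 56% of data sets, against 27% with the overall LR test. But each must still reach p<0.05 to stay, so 56% is not a rate of false predictors reported.

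Finally, the analysis is exploratory, and the convergence row would alert a reader to a failed fit. That row still leaves open what is done with the covariate.

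**Conclusion.** The concern holds as a conditional one. The SAP leaves the screening test, the p-value for a multi-level covariate and the handling of separation unstated. If the Wald p-value is used, a two-level predictor with no failures in one level is dropped at p of about 0.99 whatever its strength. For three or more levels the outcome depends on the reference level and on how level p-values are combined.

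The loss is large when SVR12 is about 96% or higher with few patients counted as failures for missing data, or when levels or subgroups are small (27% v 95%, and 17% v 84% for 40 v 40). It nearly disappears for two equal groups at the planned 90% (83% v 85%) or with 5% missing as failure (66% v 68%). These figures rest on assumed rates and splits.

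A reader might go further and conclude that the study would report genotype as not predictive. The documents do not support that as a forecast: it needs the Wald test, an empty level and no action on the convergence flag.

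**What to change.** In SAP section 9, state that each covariate is screened on one overall likelihood-ratio p-value with df = number of levels minus 1. PROC LOGISTIC already prints it as the global test of a one-covariate model. Add that row to Table 2.2.1.1.1 and keep the level odds ratios as description.

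State also that a covariate whose convergence status indicates separation is judged on this p-value and is not dropped on a Wald p-value, either in the screen or in backward elimination. Report its odds ratio by Firth penalised likelihood.

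The cost is a few sentences in the SAP, one shell row and minor extra programming, including a short macro if backward elimination is to use the likelihood-ratio criterion. No new data are needed, and the analysis stays exploratory.

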**P15-743 (HCV RWE) \_ STATISTICAL ANALYSIS PLAN \_ final 2.0 \_ 02 Feb 2018**

Abbvie LLC  
P15-743 (HCV RWE)  
**Table 2.2.1.2. SVR12 achieving response. Multiple logistic regression results**  
The core population  
Page X of X

| Patients for analysis (n) |                       | Overall               |
|---------------------------|-----------------------|-----------------------|
| [Predictor name]          |                       | XXX                   |
| OR (95% Wald CI)          | X.XXX (X.XXX - X.XXX) |                       |
| p-value                   | 0.XXXX                |                       |
| [Predictor name]          |                       | X.XXX (X.XXX - X.XXX) |
| OR (95% Wald CI)          |                       | 0.XXXX                |
| p-value                   |                       | ...                   |

SVR12: sustained virological response at 12 weeks after EoT.  
Table for the core population with sufficient follow-up data is the same table for the core population because the core population and the The core population with sufficient follow-up data are equal (contain exactly the same subjects).

Program code, date, time Data extracted: DD.MM.YYYY

Similar to tables 2.2.1.1-2.2.1.2, tables 2.2.X.X for the following subgroups will be constructed:

- with/without Ribavirin;
- Child Pugh class A/B/C;
- with/without treatment experienced.

Similar to tables 2.2.X.X, tables 2.3.X.X for the target population and tables 2.4.X.X for the core population with sufficient follow-up data will be constructed.

**P15-743 (HCV RWE) \_ STATISTICAL ANALYSIS PLAN \_ final 2.0 \_ 02 Feb 2018**

**Quality of life analysis**

**EQ-5D-5L**

**Mobility**

AbbVie Ltd  
P15-743  
**Table 3.1.1.1 EQ-5D-5L. Mobility. Descriptive statistics**  
The core population  
Page X of X

| Visit                       | ABBVIE REGIMEN + RBV          |           | ABBVIE REGIMEN - RBV          |           | Overall
(N = XX)
n (%) |
|-----------------------------|-------------------------------|-----------|-------------------------------|-----------|------------------------------|
|                             | 12 weeks
(N = XX)
n (%) |           | 12 weeks
(N = XX)
n (%) |           |                              |
| Baseline                    |                               |           |                               |           |                              |
| n                           | XX                            | XX        | XX                            | XX        | XX                           |
| Level 1 (no problem)        | XX (XX.X)                     | XX (XX.X) | XX (XX.X)                     | XX (XX.X) | XX (XX.X)                    |
| Level 2 (slight problems)   | XX (XX.X)                     | XX (XX.X) | XX (XX.X)                     | XX (XX.X) | XX (XX.X)                    |
| Level 3 (moderate problems) | XX (XX.X)                     | XX (XX.X) | XX (XX.X)                     | XX (XX.X) | XX (XX.X)                    |
| Level 4 (severe problems)   | XX (XX.X)                     | XX (XX.X) | XX (XX.X)                     | XX (XX.X) | XX (XX.X)                    |
| Level 5 (extreme problems)  | XX (XX.X)                     | XX (XX.X) | XX (XX.X)                     | XX (XX.X) | XX (XX.X)                    |
| EoT                         | ...                           | ...       | ...                           | ...       | ...                          |
| SVR12                       | ...                           | ...       | ...                           | ...       | ...                          |
| SVR24                       | ...                           | ...       | ...                           | ...       | ...                          |

N: the number of subjects in the core population.  
n: the number of valid measurements.  
EoT: end of treatment.  
SVR12: sustained virological response at 12 weeks after EoT.  
SVR24: sustained virological response at 24 weeks after EoT.  
Percentages are calculated from the number of subjects in the core population.

Program code, date, time

Data extracted: DD.MM.YYYY

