9.7.5 Patient Questionnaires

The EQ-5D-5L is a health state utility instrument that evaluates preference for health status (utility). The EQ-5D-5L comprises 5 dimensions (mobility, self-care, usual activities, pain/discomfort, anxiety/depression) each of which are rated on 5 levels of

Confidential Information

No use or disclose outside AbbVie is permitted without prior written authorization from AbbVie

Version 3.0 (22 Apr 2015) – country v 1.0 dated 26.06.2015

Page 37 of 61

severity (1: indicating no problem, 2: indicating slight problems, 3: indicating moderate problems, 4: indicating severe problems, 5: indicating extreme problems), and a separate VAS.

Patients' responses to the EQ-5D-5L will be combined into a unique health state using a 5-digit code with one digit from each of the 5 dimensions representing the level of severity. These EQ-5D-5L states will be converted into a single preference-weighted health utility index score by applying country-specific weights (if available) or US weights (if not available).

No imputation will be performed for missing items, and in case of missing items no index score will be calculated.

A summary table will show descriptive statistics (n, mean, median, SD, minimum and maximum) of the index score values and for the VAS values for baseline and the post-baseline time points, as well as changes from baseline both for the index score values and for the VAS values. In addition analysis of covariance (ANCOVA) will be applied to investigate the effect of the different ABBVIE REGIMENS (\pm RBV and duration) on EQ-5D-5L endpoints using the corresponding EQ-5D-5L baseline values as covariates.

Assessments of work productivity and activity impairment as assessed by the WPAI Hep C v2.0 will be evaluated according to the WPAI-SHP scoring manual. The WPAI yields four types of scores, the results of which will be presented as percentage of impairment from 0 to 100. Higher percentages indicate greater impairment:

1. % absenteeism: percentage of work time missed due to hepatitis C
2. % presenteeism: percentage of impairment while working due to hepatitis C
3. % TWP: percentage of overall work impairment due to hepatitis C
4. % TAI: percentage of general (non-work) activity impairment due to hepatitis C

The WPAI Hep C v2.0 consists of 6 questions aimed at the following targets:

- Q1. currently employed (yes, no)
- Q2. hours missed due to hepatitis C in the last seven days

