## **7 Statistical considerations**

### **7.1 Standard descriptive statistics**

The data of continuous type will be presented with following statistics:  $n$  (the number of subjects with non-missing data), mean, median, standard deviation (SD), interquartile range (IQR), minimum and maximum values. In quantitative tests the values less than LLoQ will be replaced to 1/2 of LLoQ, the values more than ULoQ will be replaced to ULoQ.

The data of categorical type (including clinical evaluations) will be presented with  $n$  (the number of subjects with no missing data), frequencies and percentages. Unless otherwise specified, percentages by categories will be based on the number of subjects with no missing data.

Confidence intervals will be calculated for all effectiveness endpoints and questionnaires results.

The number of decimals for each descriptive statistical value will be determined by the following rules:

- mean, median and IQR: +1 decimal place compared to the analyzed variable values;
- standard deviation: +2 decimal places compared to the analyzed variable values;
- minimum and maximum values: the same as for the analyzed variable values;
- percentages (including CI) will be rounded to one decimal place.

The maximum number of decimal places in the statistical report is four. If some descriptive statistical value has more than four decimal places after above mentioned rules application, this value will be rounded to four decimal places .

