## 10 Quality of life analysis

Patient questionnaires analysis will be conducted on *the core population (CP)*, *the target population (TP)* and *the core population with sufficient follow-up data (CPSFU)*.

The results will be reported overall and for scheduled treatment combination ( $\pm$  RBV) and duration (12 or 24 weeks) groups.

Tables with descriptive statistics for baseline and post-baseline time points will be prepared for each questionnaire results in accordance with section 7.1. Confidence intervals will be presented according the section 7.2. All corresponding listings will be presented. Additional listings for *the non-core population (NCP)* will be created.

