| Platelets        |  |  |                     |
| n                | XXX  | XXX  | XXX                 |
| Normal           | XX (XX.X)                                    | XX (XX.X)                                    | XX (XX.X)           |
| Abnormal NCS     | XX (XX.X)                                    | XX (XX.X)                                    | XX (XX.X)           |
| Abnormal CS      | XX (XX.X)                                    | XX (XX.X)                                    | XX (XX.X)           |
| Prothrombin time |  |  |                     |
| n                | XXX  | XXX  | XXX                 |
| Normal           | XX (XX.X)                                    | XX (XX.X)                                    | XX (XX.X)           |
| Abnormal NCS     | XX (XX.X)                                    | XX (XX.X)                                    | XX (XX.X)           |
| Abnormal CS      | XX (XX.X)                                    | XX (XX.X)                                    | XX (XX.X)           |

N: the number of patients in the safety population.  
n: the number of valid measurements. Percentages are based on the number of valid measurements at analyzed visit.

CONFIDENTIAL AND PROPRIETARY

Data MATRIX Ltd.

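### Categorical questionnaire tables divide by the fixed population N at every visit, so every category percentage shrinks as forms go missing

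*SAP*

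**What the plan says.** The five-level EQ-5D-5L shell (SAP Table 3.1.1.1) has one N per column, placed in the header, and a separate n row for each of Baseline, EoT, SVR12 and SVR24. Its notes define "n: the number of valid measurements" and then state "Percentages are calculated from the number of subjects in the core population". The same denominator note stands under:

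- the dichotomised EQ-5D-5L table (3.1.2.1);
- WPAI Q1, current employment (3.8.1);
- the PAM-13 item table (3.12.1) and the PAM-13 activation level table (3.12.16).

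The other four EQ-5D-5L dimensions, the remaining PAM-13 items, and the target-population and CPSFU versions are to be built in the same way. None of these shells has a row for missing forms.

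The SAP text points elsewhere. SAP 7.1 says "Unless otherwise specified, percentages by categories will be based on the number of subjects with no missing data". SAP 10 says "Tables with descriptive statistics for baseline and post-baseline time points will be prepared for each questionnaire results in accordance with section 7.1". The repeated-visit laboratory shell (Table 4.5.2) states "Percentages are based on the number of valid measurements at analyzed visit". SAP 7.1 adds "Confidence intervals will be calculated for all effectiveness endpoints and questionnaires results", so the denominator also matters for interval estimates. For EQ-5D-5L, Protocol 9.7.5 states "No imputation will be performed for missing items, and in case of missing items no index score will be calculated"; nothing fills the gap left by a form that is not returned.

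**The concern.** A fixed denominator is harmless in a baseline table with little missing data. In a table meant to be read across visits, it mixes two quantities: what patients answered and how many answered. If completion declines, the share reporting problems falls, the share reporting none falls with it, and so do both the employed and the not-employed shares. If completion differs between the columns with and without RBV, a between-regimen difference appears for the same reason.

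Missing forms are foreseeable. Protocol Table 2 limits collection to data available from routine practice. Protocol 9.9 names missing data as a limitation. SAP Table 1.2 lists failure to return and withdrawn consent among its reasons. EQ-5D-5L and WPAI run to 24 weeks after treatment. A PAM-13 activation level can be lost even when the form is returned, because SAP 10.4 gives no score when fewer than ten items are answered.

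The secondary objective at stake is to document the effect of the regimen on PROs and work productivity. These frequency tables are the planned summaries over time of the five EQ-5D-5L dimensions, employment status and activation level.

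**Working it through.** **Inputs.** The documents give no questionnaire completion rate and no expected share with problems. The only related figure is the study size of 158 (Protocol 9.5, SAP 4.2), used here as an illustrative core-population N. That figure reproduces: the exact 95% interval at a rate of 90% with 158 patients is 84.23 to 94.20, width 9.97 points (157 patients give 10.01), matching the stated 84.2 to 94.2.

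**Assumptions.** N = 158; the true share with problems is constant at 40%; missingness is unrelated to health status; completion ranges from 100% down to 60%.

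**Formulas.** With x patients in a category and n valid forms at the visit:

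- shell percentage = 100·x/N
- valid percentage = 100·x/n
- hence shell percentage = valid percentage × (n/N)

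The factor n/N is the completion rate. It applies equally to every category, so the categories sum to 100·n/N.

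**Results for the dichotomised EQ-5D-5L table.**

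| Completion | n | x with problems | Shell: problems | Shell: no problem | Sum of rows | Valid: problems |
|---|---|---|---|---|---|---|
| 100% | 158 | 63 | 39.9% | 60.1% | 100.0% | 39.9% |
| 90% | 142 | 57 | 36.1% | 53.8% | 89.9% | 40.1% |
| 80% | 126 | 50 | 31.6% | 48.1% | 79.7% | 39.7% |
| 70% | 111 | 44 | 27.8% | 42.4% | 70.3% | 39.6% |
| 60% | 95 | 38 | 24.1% | 36.1% | 60.1% | 40.0% |

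**Other true shares, at 70% completion.** A true 20% prints as 13.9% (22/158) against 19.8% on valid forms (22/111). A true 60% prints as 42.4% (67/158) against 60.4% (67/111).

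**A change can reverse.** If the true share rises from 40% to 45% and completion is 80%, the shell prints 57/158 = 36.1%, an apparent fall. On valid forms it is 57/126 = 45.2%.

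**Intervals.** The shells have no interval column, but SAP 7.1 and 10 call for intervals. At 70% completion the Clopper-Pearson interval is 21.0 to 35.5% for 44/158, which excludes the assumed 40%, and 30.5 to 49.4% for 44/111.

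**Visits exposed.** Protocol Table 2 collects EQ-5D-5L and WPAI at baseline, EoT, SVR12 and SVR24, and their shells follow that schedule. PAM-13 is collected at baseline and EoT only, and its shells show only those two visits. With 95% completion at EoT, a 40% category of a PAM-13 table would print as 60/158 = 38.0% instead of 60/150 = 40.0%.

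**The case against.** SAP 7.1 lets a table specify another denominator, and the footnotes do so. Departing from the default is therefore not an error in itself. This stands, but no reason is given, SAP 10 sends these same tables back to 7.1, and the identical footnote sits on one-time baseline shells such as Tables 1.4.1 and 1.5.1. It may simply have been carried over.

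The shells also disclose what is needed to undo the effect. N, the visit-level n and the category counts are all printed, so a careful reader can recompute. This stands and limits the harm, although the percentages are what will usually be quoted.

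The quantitative PRO summaries do not use this denominator: EQ VAS, EQ-5D-5L index, the four WPAI scores, the PAM score and the ANCOVAs. This also stands.

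The loss may be small. Footnotes to the effectiveness shells (Table 2.1.1.1.1, for example) describe the core population and the CPSFU as identical, which would mean few patients without late HCV RNA data. That does not settle the matter: the CPSFU is defined by HCV RNA data and not by questionnaires, and the note following Table 2.1.1.1.3 treats the equality as conditional.

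A reader might go further and infer that the tables will show a spurious health improvement of some 12 points by SVR24 (39.9 − 27.8 = 12.1). The documents do not support that as an expectation. It needs 70% completion, which is an assumption. The no-problem row falls at the same time and the two rows visibly sum to 70%, so the table signals missing data more than it signals improvement. Falling problems as a favourable signal is a reading open only for EQ-5D-5L. For employment and PAM-13 the effect is a loss in all categories, and PAM-13 has no post-treatment visit over which to lose forms.

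**Conclusion.** The point holds as a conflict between the shells and the SAP text that, if programmed as drafted, gives misleading percentages whenever forms are missing. The relation is exact: printed percentage equals percentage among completed forms times completion rate. The size is conditional. It is nil with complete forms. For a constant 40% with problems it is about 4 points at 90% completion (39.9 to 36.1), 8 at 80% (39.9 to 31.6) and 12 at 70% (39.9 to 27.8). These figures assume N = 158, full completion at baseline and missingness unrelated to health status; the completion rates are not in the documents.

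It would be going too far to say that the PRO objective as a whole is compromised. The affected outputs are secondary frequency tables with no test attached, the score-based analyses are untouched, and the primary endpoint is not involved. This is a should-fix.

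**What to change.** In Tables 3.1.x to 3.5.x, 3.8.1, 3.12.1 to 3.12.13 and 3.12.16, and in their target-population and CPSFU copies (including 3.9.1, 3.10.1, and the matching 3.13 and 3.14 tables):

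- replace the denominator footnote with one saying that percentages are based on the number of valid questionnaires (n) at that visit;
- add a row at each visit with the count of missing forms, N − n;
- for the PAM-13 items, state whether an N/A response counts in n, since the shell lists it as a category;
- use the same n for any confidence interval on these percentages.

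The cost is a footnote edit and a small programming change, with no new data. SAP 2 allows revision before the database soft lock and asks for later departures to be explained in the study report.

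This corrects the denominator only. If patients in poorer health are less likely to return forms, the valid percentages remain biased. The missing row shows how far that could matter but does not remove it.
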